## e. Measures

We plan to use the following instruments for data collection:

- Structured Clinical Interview for DSM-5 (SCID-5)
- Hamilton Depression Rating Scale (HAM-D)
- Montgomery-Asberg Depression Rating Scale (MADRS)
- Columbia Suicide Severity Rating Scale (C-SSRS)
- Clinical Global Impressions Scale (CGI) severity of illness subscale (CGI-S)
- Beck Anxiety Inventory (BAI
- Young Mania Rating Scale (YMRS)
- Discontinuation-Emergent Signs and Symptoms checklist (DESS)
- Serotonin Syndrome Screening-Hunter Criteria
- Eosinophilia-Myalgia Syndrome Screening
- Eosinophilia-Myalgia Participant Information Sheet
- Serotonin Syndrome Participant Information Sheet
- National Cancer Institute Diet History Questionnaire Version II (DHQ-II)
- Antidepressant Treatment Response Questionnaire (ATRQ)

**f. Potential Risks:** During the screening visit, participants may become emotionally upset when asked about their psychiatric history including suicide attempts, or physical and sexual abuse.

Participants may also experience discomfort when providing urine for pregnancy tests. It is possible that a participant's illness could worsen during the study. This could be related or unrelated to the study. If the participant's illness worsens to the point that they are a danger to herself or others, they will be referred for appropriate care. If the participant is hospitalized for worsening illness, they will be withdrawn from the study. Participants may experience gastrointestinal discomfort as a result of taking creatine or 5-HTP. Participants will be encouraged to take both medications with food to minimize this risk. Finally, as detailed above, supplementation with 5-HTP increases the risks of eosinophilia-myalgia syndrome and serotonin syndrome. Notably, in our pilot study, there were no serious adverse events attributable to the study drugs. Participants will be counseled about these risks, informed of the signs and symptoms of these conditions, provided with information sheets detailing the symptoms of these disorders in lay terms and describing steps to take for further evaluation if indicated, and will be screened for both conditions at each visit after the initiation of treatment.

MRI/MRS scans do not use ionizing radiation like x-rays or CT scans. Instead, magnetic fields and radio waves are used to take the pictures. There are no known risks related to MRI scans – other than the risk of injury when metallic objects are brought into the scanning room by mistake. Serious injury can occur during an MRI scan to persons who have:

- Cardiac (heart) pacemakers.
- Metal clips on blood vessels (also called stents).
- Artificial heart valves.
- Artificial arms, hands, legs, etc.
- Brain stimulator devices.
- Implanted drug pumps.
- Cochlear (ear) implants.
- Ocular (eye) implants or known metal fragments in eyes.
- Exposure to shrapnel or metal fillings
- Other metallic surgical parts.
- Orthodontic braces on the teeth.
- Body jewelry or piercings that cannot be removed for the scan.
- Certain tattoos with metallic ink
- Certain transdermal (skin) patches such as NicoDerm (nicotine for tobacco dependence),
- Transdermal scopolamine or Ortho-Evra (birth control)

If the participants have any such devices, or has had a surgery where metal devices were placed in their body, they cannot take part in the study unless cleared for MRI scanning by the surgeon who implanted the medical device(s).

Serious risks exist if ferromagnetic objects (things that stick to magnets) are brought into the scanning area. These items can become dangerous flying objects and are not allowed near the MRI scanner. The FDA has approved the 3T scanner for routine clinical studies. The FDA has decided that MRI machines of 8T or less do not pose a risk. Although the scans we are using in this study have no known risks, there could be ill effects that are delayed, such that they have not yet been recognized by the FDA. The brain scans do not cause pain. Apart from the scanner noise, the participant will not know the scan is taking place. Inside the scanner, some people experience claustrophobia (fear of being in small spaces), dizziness, headaches, or a metallic taste in the mouth. Some people experience double vision or see flashing lights. These symptoms are temporary, and will stop when the participant leaves the scanner. The participant may feel cramped inside the scanner. There is a mirror placed inside the scanner so the subject can see his or her face, and look out into the scanning room. The technologist will be able to hear the participant at all times. Very rarely, someone having an MRI scan feels a tingling in his or her back. This is due to the magnetic field changing quickly during the scan. The precautions taken will avoid all the known risks related to MRI scans. The participant can stop the scan at any time.

Finally, there is a small risk that subjects' protected health information will be lost or misappropriated during the study.

## g. Adequacy of Protection against Risks

**h. Recruitment:** Subjects will be recruited through radio advertisements broadcast on local radio networks. We will also contact eligible participants who have indicated an interest in research participation who have listed themselves in the Department of Psychiatry research recruitment database. Additionally, we will contact outpatient providers in the Department of Psychiatry to apprise them of the study so that they can refer patients (no referral fees will be offered), and these providers will be sent digital copies of the flyer via email. Clinical participants will be compensated a total of \$235 in cash to account for travel expenses and time. Compensation will be given using the schedule below. Per-visit compensation is based on the estimated time for each visit (at least one hour) and is judged not to represent an undue inducement. Study participants may choose to skip being compensated at some visits and then be compensated in lump sums.

- 1. \$25 Screening
- 2. \$65 Baseline visit (includes \$50 compensation for MRI)
- 3. \$15 Treatment phase visits (weeks 1, 2, 4, 6)
- 4. \$65 Treatment week 8 (includes \$50 compensation for MRI)
- 5. \$10 Follow-up visits (weeks 10, 12) (total \$20)

**i. Informed Consent:** Consent will be obtained before any study procedures are initiated. Potential participants will be informed of the study and offered a consent form to review. They will be encouraged to discuss study participation with their relatives. If a potential participant expresses interest in study participation, the informed consent process will be conducted. After the informed consent process, individuals will be offered time to consider study participation and to ask questions. Subjects will have the opportunity to discuss the study with a study team member in a setting free of coercion. The language of the informed consent form is written at a level easily understood by the subject and any questions asked by the subject will be answered honestly and free of bias. A specific meeting time will be set up between a study team member and the participant where the entire informed consent document will be carefully explained in its entirety. The length of the meeting will be designed so there is the necessary amount of time for all questions to be answered. Subjects will be separately consented for blood sample storage for later genetic testing and will be allowed to opt-out of this procedure while still participating in the other aspects of the study.

**j.** Screening for Serotonin Syndrome: Given the potential development of serotonin syndrome in patients taking multiple serotonergic medications (in this study, an SSRI plus 5-HTP), monitoring for serotonin syndrome is an important element of participant safety. There are no widely-used standardized scales for the assessment of serotonin syndrome, but algorithms for the detection and diagnosis of the condition exist . As noted above, subjects will have vital signs performed at each visit. Participants will also be asked about symptoms of serotonin syndrome at each visit. In our pilot study, a physician completed a thorough physical exam for each patient to screen for these symptoms, but no cases of serotonin syndrome were required and this approach was deemed to be inefficient. Accordingly, in the currently proposed study, we will have a physician on call during each patient visit to complete a physical exam and further assessment for serotonin syndrome if there are vital sign abnormalities or symptoms (severe diarrhea or nausea, sweating, shakiness, stiffness, confusion) that are suggestive of serotonin syndrome. In such cases, the clinician will assess for ocular clonus, mydriasis, diaphoresis, rigidity,

hyperreflexia, and clonus, and will evaluate the likelihood of serotonin syndrome using the Hunter Criteria. Finally, at the baseline visit subjects will receive an information sheet describing signs and symptoms of serotonin syndrome in lay terms and providing instructions on how they should seek further evaluation if those symptoms are evident.

**k.** Screening for Eosinophilia-Myalgia Syndrome: No standardized measures for the detection of eosinophilia-myalgia syndrome (EMS) exist. In this study, participants will be informed about the symptoms of EMS, and will be provided with an information sheet describing the symptoms of EMS in lay terms and providing instructions on how they should seek further evaluation if those symptoms arise. They will be asked about symptoms that may be indicative of EMS (especially myalgias) at each treatment and follow-up visit. At the screening visit, a CBC with automated differential will be performed to screen for pre-existing eosinophilia. Although in principle participants could receive a complete blood count at each visit after the initiation of treatment to screen for the development of EMS, to our knowledge there is no published data to support this intervention and the presence of eosinophilia in the absence of clinical symptoms is not likely to be specific for EMS. In our pilot study, subjects received a physical exam at each visit to screen for symptoms of EMS, but this was found to be an inefficient measure. Accordingly, in the currently proposed study a physician will be on call during each patient visit to complete a physical exam and further assessment for EMS if there are vital sign abnormalities or symptoms (rash, other skin changes, hair loss, muscle aches, joint pain, shortness of breath) that are suggestive of EMS.

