After the screening visit, participants will have a **baseline** visit after one week with the MRI happening + 4 days from the baseline visit, prior to the start of treatment. At the baseline visit, the HAM-D17, MADRS, C-SSRS, BAI, YMRS, and CGI-S will be administered. Vital signs will be checked and a physical exam performed if patient symptoms indicate a need. Whole blood serotonin will be drawn. Subjects will be asked to be fasting for at least 3 hours prior to the blood draw. The blood draw will occur between 2 and 5pm to minimize circadian variation in serotonin levels. Participants will be evaluated for serotonin syndrome using the Hunter Criteria. Baseline P-MRS and resting state fcMRI will be completed. After initiation of treatment, **subjects will be** reevaluated at 1, 2, 4, 6, and 8 weeks (+3 days). At each these visits, the HAM-D17, MADRS, C-SSRS, BAI, YMRS, and CGI-S will be administered again. Subjects will be asked to be fasting for at least 3 hours prior to the blood draw. Whole blood serotonin will be drawn. The blood draw will occur between 2 and 5pm to minimize circadian variation in serotonin levels. Follow-up P-MRS and resting state fMRI will be completed at week 8. Vital signs with pulse oximetry, focused physical exam if indicated, collection of urine for pregnancy screening if indicated, recording of concomitant medications, self-reported drug use, medication compliance assessment, study medication dispensing, and screening for treatment-related adverse effects will also be undertaken. Screening for treatment-related adverse effects will include application of the Hunter Criteria for serotonin syndrome as well as evaluation for symptoms of eosinophilia-myalgia syndrome. If subjects exhibit symptoms of eosinophilia-myalgia syndrome, a CBC with automated differential will be obtained. Finally, participants will be seen for follow up visits at 2 weeks and 4 weeks (+3 days) after completion of 5-HTP/Cr supplementation. Measure at these visits will include the HAM-D17, MADRS, C-SSRS, BAI, YMRS, CGI, DESS, vitals with pulse oximetry if indicated, focused physical exam if indicated, and evaluation for serotonin syndrome and EMS. Again, if symptoms of EMS are present, a CBC with automated differential will be obtained. After the screening visit. Participants can request study visits by videoconference with the exception of briefly dropping by the clinic for a blood draw and/or MRI as indicated in the schedule below.

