
	Screening	Baseline	Treatment					Follow-up		
Week	-1	0	1	2	4	6	8	10	12	
SCID-I	Х									
HAM-D17	Х	Х	Х	Х	Х	Х	Х	Х	Х	
MADRS	Х	Х	Х	Х	Х	Х	Х	Х	Х	
C-SSRS	Х	Х	Х	Х	Х	Х	Х	Х	Х	
BAI	Х	Х	Х	Х	Х	Х	Х	Х	Х	
CGI-S	Х	Х	Х	Х	Х	Х	Х	Х	Х	
YMRS	Х	Х	Х	Х	Х	Х	Х	Х	Х	
DESS								Х	Х	
Medical History	Х									
Diet History Questionnaire II	Х									
ATRQ	Х									
Hunter criteria		Х	Х	Х	Х	Х	Х	Х	Х	
Screening for EMS			Х	Х	Х	Х	Х	Х	Х	
Side-effect screening			Х	Х	Х	Х	Х			
Pregnancy test**	Х	Х	Х	Х	Х	Х	Х			
BUN/Creatinine	Х									
CBC with differential	Х		Х*	X*	X*	X*	X*	X*	X*	
Whole-blood 5-HT (fasting for > 3 hours; drawn	Х	Х	Х	Х	Х	Х	Х			
between 2:00 and 5:00pm										
EKG	Х									
Vitals including pulse-oximetry	Х	Х	Х	Х	Х	Х	Х	Х	Х	
Focused physical exam	Х		Х*	X*	X*	X*	Χ*	X*	X*	
Review of current medications	Х	Х	Х	Х	Х	Х	Х			
 P-MRS		Х					Х			
Resting State fMRI		Х					Х			

Table 2. Study Procedures for Clinical Subjects

\* = only if clinically indicated by presence of adverse symptoms or symptoms suggestive of EMS or serotonin syndrome

\*\* = all female subjects, unless reporting menopause, hysterectomy, tubal ligation or currently using an intrauterine device (IUD)

Once entered into the study, participants will be 1:1:1:1 randomized to receive either Cr+ placebo, 5-HTP+placebo, 5-HTP+Cr, or placebo+placebo. Block randomization using a SAS code, PROC PLAN with Block, will be used to ensure equal treatment allocation within each block. The study will be conducted as a double-blind trial, with neither participants nor research staff aware of participant assignment. Except in cases of medical emergency, the double-blind will not be "broken" until recruitment is closed and the final participant has completed 8 weeks of treatment and 4 weeks of follow-up. We anticipate an attrition rate of ~20% based on our pilot study (where attrition was 13%), and so will plan to recruit a total of 75 subjects, for a total recruitment of 60 subjects. The blind will be broken following the culmination of the study or at the request of a medical professional dealing with a medical emergency in a case in which it would help a study participant.

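### No itemised EMS or side-effect symptom record is scheduled before the first dose, and no DESS before treatment stops, so old complaints cannot be reliably told from new ones

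*Combined protocol and SAP*

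**What the plan says.** Three symptom instruments are involved, and the text and Table 2 agree on their timing.

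- **EMS screening.** Section k: "They will be asked about symptoms that may be indicative of EMS (especially myalgias) at each treatment and follow-up visit". Section f (Potential Risks) says of serotonin syndrome and EMS that participants "will be screened for both conditions at each visit after the initiation of treatment". In Table 2 the row "Screening for EMS" is blank at weeks -1 and 0 and marked at weeks 1, 2, 4, 6, 8, 10 and 12.
- **Side effects.** The Table 2 row "Side-effect screening" is blank at weeks -1 and 0 and marked at weeks 1, 2, 4, 6 and 8.
- **DESS.** Table 2 marks it at weeks 10 and 12 only. Section c lists it among the follow-up measures: "CGI, DESS, vitals with pulse oximetry if indicated, focused physical exam if indicated, and evaluation for serotonin syndrome and EMS".

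The response to EMS symptoms is also stated. Section c: "If subjects exhibit symptoms of eosinophilia-myalgia syndrome, a CBC with automated differential will be obtained". Section k has an on-call physician examine a participant who has abnormal vital signs or suggestive symptoms, which it lists as "rash, other skin changes, hair loss, muscle aches, joint pain, shortness of breath". Neither passage mentions whether the symptom was there before treatment.

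**The concern.** The listed EMS symptoms are common and non-specific, and every participant is already taking an SSRI or SNRI. Someone with long-standing muscle aches who mentions them at week 1 may be sent for examination and a blood count. Nothing in the schedule provides a written pre-dose answer to the same question for comparison. A DESS item reported at week 10 has the same difficulty: it may have been present throughout treatment.

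This matters more here because section k relies on symptom enquiry and vital signs to start EMS assessment. It explains why routine on-treatment blood counts were not adopted, and it replaces the pilot study's examination at every visit with one on indication. Section c allows a research assistant to run visits and lets participants ask for videoconference. Under the adverse events section, the investigators judge whether an event is related to the research. Without a written reference, that judgement depends on recall, after participants have been told which EMS symptoms to look for.

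**Working it through.** The plan states no figure on this point, so the main check sets its provisions side by side.

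**1. Is there a reference measurement before the relevant exposure change?**

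| Instrument | Change of interest | Last scheduled record before it (Table 2) | First record after it |
|---|---|---|---|
| Hunter criteria | first dose | week 0 | week 1 |
| EMS screening | first dose | none | week 1 |
| Side-effect screening | first dose | none | week 1 |
| DESS | end of treatment | none | week 10 |

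The plan takes a pre-dose reference for one of its two named 5-HTP syndromes and not for the other.

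**2. Do other pre-dose data supply it?**

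- Medical history at screening (section c): its stated focus is illnesses and treatment, not individual symptoms.
- Focused physical at screening, and at baseline if symptoms call for it (section c): records signs, and could note a rash. It is not an item-by-item enquiry.
- Screening blood count with differential (section k): gives a reference for eosinophils, not for aches or hair loss.
- Vital signs with pulse oximetry at weeks -1 and 0 (Table 2): bear on shortness of breath only.
- Exclusion of pulmonary disease, fibromyalgia, rheumatological conditions and eosinophilia (Table 1): removes diagnoses, not everyday aches or joint pain.
- For DESS, the week 8 side-effect, EMS and Hunter screens are a partial on-treatment record, but not the same checklist.

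The gap is narrowed, not closed.

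**3. Is there a rule for what counts as emergent?** None was found. The statistical section covers spectroscopy, resting-state imaging and blood serotonin. The documents do not define a treatment-emergent event or say how EMS symptoms, side effects or DESS items are scored or analysed.

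**4. How large could this be?** Illustration only. Inputs: 60 participants, 15 per group (power section), and an assumed proportion p with at least one listed symptom before dosing.

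- Expected number with such a symptom = 60 × p.
- Chance of at least one = 1 − (1 − p)^60.
- Chance that two given arms differ by 3 or more = sum of P(a)P(b) over |a − b| ≥ 3, with a and b independent Binomial(15, p).

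| p | Expected of 60 | At least one | Two arms differ by 3 or more |
|---|---|---|---|
| 5% | 3 | 95.4% | 3.8% |
| 10% | 6 | 99.8% | 12.1% |
| 20% | 12 | >99.9% | 24.9% |
| 30% | 18 | >99.9% | 31.8% |

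At the planned enrolment of 75, p = 10-30% gives 7.5-22.5 expected. One misattributed participant moves an arm's symptom rate by 1/15 = 6.7 percentage points, and two move it by 2/15 = 13.3.

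These are counts of people who have a symptom. They are not counts of people worked up, because section k asks whether symptoms suggest EMS, which leaves room for judgement.

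**The case against.** The case against has real force, and most of it limits what can be claimed.

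- **Counting.** A reader might infer that pre-existing symptoms will be counted as emergent, or that discontinuation rates will be inflated. The documents contain no counting rule, so neither is established. What they show is that the means to separate old from new is missing.
- **Withdrawal.** A reader might infer that background aches will lead to withdrawal. Table 1 and section b require evidence of EMS, or side effects of the intervention that are intolerable or clinically significant. Before that come a physician's assessment and a blood count that can be compared with the one at screening. DESS is given after treatment ends and cannot lead to treatment withdrawal.
- **Symptoms as the only signal.** Abnormal vital signs also trigger assessment, and they have pre-dose values.
- **Bias between arms.** Allocation is randomised, double-blind and placebo-controlled, so pre-existing complaints fall on the arms by chance. In arm comparisons they are mainly noise.
- **Unseen forms.** The Measures section only names the EMS screening form and DESS. They may ask about onset, and the physician certainly can.
- **Proportion.** This is a proof-of-concept trial sized on imaging, and a sensitive EMS trigger may be deliberate.

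What remains is that an onset question asked after dosing is retrospective. None of the partial safeguards is scheduled as an itemised symptom record taken before exposure, and the week 0 answer cannot be recovered once dosing begins.

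**Conclusion.** The point holds as a gap in the measurement schedule. It weakens attribution of symptoms in individual participants and estimates of within-arm incidence, and it may cause some avoidable EMS work-up. The DESS part is the weaker one: it affects only the interpretation of symptoms at weeks 10 and 12.

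The timing finding rests on Table 2 and on text that agrees with it. The size rests on an assumed prevalence with no source in the documents, and on the forms having no adequate onset item. If the forms do record onset, the gap is smaller. No effect on the imaging or serotonin analyses is claimed. This is a modest but worthwhile correction, and it has to be made before participants are dosed.

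**What to change.** 1. In Table 2, mark EMS screening and side-effect screening at week 0, completed before the first dose, and mark DESS at week 8. Bring the wording of sections c, f and k on when the enquiries are made into line.
2. Add a reporting rule: side effects and EMS symptoms are counted when new or worse than at week 0, and DESS items when new or worse than at week 8.
3. Leave the section k trigger for physician assessment and blood count unchanged. The new records inform attribution and reporting; they do not alter any clinical threshold.

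The cost is a few extra minutes for each participant at two existing visits, with no new visit or blood draw. For participants already dosed, the week 0 record cannot be recreated, and their reports should be identified as lacking it.

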# I. Adverse events

Unanticipated problems and adverse events that are related to the research, or which place participants at greater-then-expected risk, will be reported to the Institutional Review Board (IRB) within ten working days of the event. *Unanticipated problems* involving risk to participants or others are defined as any incident, experience or outcome that meets the following criteria:

- Unforeseen (not expected by the researcher or the research participant) given the research procedures and the subject population being studied;
- Related or probably related to participation in the research, or if the event or problem probably or definitely affects the safety, rights and welfare of current participants; and
- Suggests that the research places participants or others at a greater risk of harm (includes physical, psychological, economic or social harm) than was previously known or recognized.
- An *unexpected adverse event* is any adverse event occurring in one or more participants participating in a research protocol, whose nature, severity, or frequency is not consistent with either:
  - The known or foreseeable risk of adverse events associated with the procedures involved in the research that are described in the protocol related-documents (i.e. protocol, investigational brochure, consent form, or product labeling).
  - The expected natural progression of any underlying disease, illness or medical condition of the subject experiencing the adverse event.

The Principal Investigator will make the initial determination if an unexpected, adverse event is related or unrelated to the investigational drug or a clinical or research procedure. An adverse event is "related to the research" if in the opinion of [name] or [name], it was more likely than not related to the investigational agent or intervention.

